# 9.6.2 Baseline, Treatment (Visit 1)

Occurs within 28 days following Screening visit (Visit 0). Predose Assessments (Baseline):

- Verify inclusion/exclusion criteria
- Perform and record result of physical examination and VS

- Perform and record visual oral cavity examination and neck lymph node examination
- Perform and document baseline clinical tumor measurement
- Collect clinical labs: blood draw for CBC, chemistry panel (creatinine for determining creatinine clearance, BUN, LFT, electrolytes [potassium, magnesium, calcium, and sodium], hCG [urine] for females of childbearing potential), and perform urinalysis.
- Administer oral anti-emetics (ondansetron or promethazine, the dose to be determined at the discretion of the PI) before the start of PRV111 treatment
- Photograph the tumor
- Draw blood for PK (-15 to 0 minutes predose)
- Administer PE (refer to Pharmacy Manual for administration instructions)
  - document time of application
  - ask for taste of PE solution
- Administer PRV111 patch(es) and document time of each application and removal. Ask for taste of patch.

## **Postdose Assessments:**

- Draw blood for PK 30±5 minutes, 60±5 minutes and 120±5 minutes following application of the last patch at that treatment visit.
- VS shall be monitored at 30±5 minutes, 60±5 minutes and 120±5 minutes following application of the last patch applied.
- Collect all used patches (include the ones that detached prematurely), record the time of the detachment of each patch, store the patches in the plastic bags supplied by the Sponsor (refer to Laboratory Manual for instructions).
- Record AEs as reported by subject or observed by Investigator
- Review any concomitant therapy
- Schedule study visits

# 9.6.3 Treatment (Visit 2)

Occurs at least 48 hours, up to 144 hours, after previous visit.

#### **Predose Assessments:**

- Perform and document physical examination and VS
- Perform and document visual oral examination and neck lymph node examination
- Perform and document clinical tumor measurement and Tumor volume CFB criteria
- Administer oral anti-emetics (ondansetron or promethazine, the dose to be determined at the discretion of the PI) before the start of PRV111 treatment
- Photograph the tumor
- Draw blood for PK (-15 to 0 minutes predose)
- Administer PE (refer to Pharmacy Manual for administration instructions)
  - document time of application
- Administer PRV111 patch(es) and document time of each application and removal
  - Document adherence of each patch

#### **Postdose Assessments:**

- Draw blood for PK 30±5 minutes following application of the last patch applied at that treatment visit. VS shall be monitored at 30±5 minutes following application of the last patch at that treatment visit.
- Collect all used patches (include the ones that detached prematurely), record the time of the detachment of each patch, store the patches in the plastic bags supplied by the Sponsor (refer to Laboratory Manual for instructions)
- Record AEs as reported by subject or observed by Investigator
- Review any concomitant therapy
- Schedule study visits

## 9.6.4 Treatment (Visit 3)

Occurs at least 48 hours, up to 144 hours, after previous visit.

#### **Predose Assessments:**

- Perform and document physical examination and VS
- Perform and document visual oral examination and neck lymph node examination
- Perform and document clinical tumor measurement and Tumor volume change from baseline
- Collect clinical labs: blood draw for CBC, chemistry panel (creatinine for determining creatinine clearance, BUN, LFT, electrolytes [potassium, magnesium, calcium, and sodium], and perform urinalysis.
- Administer oral anti-emetics (ondansetron or promethazine, the dose to be determined at the discretion of the PI) before the start of PRV111 treatment
- Photograph the tumor
- Draw blood for PK (-15 to 0 minutes predose)
- Administer PE (refer to Pharmacy Manual for administration instructions)
  - Document time of application
- Administer PRV111 patch(es) and document time of each application and removal
  - Document adherence of each patch

#### **Postdose Assessments:**

- Draw blood for PK 30±5 minutes
- VS shall be monitored for 30±5 minutes following application of the last patch applied at that treatment visit
- Collect all used patches (include the ones that detached prematurely), record the time of the detachment of each patch, store the patches in the plastic bags supplied by the Sponsor (refer to Laboratory Manual for instructions).
- Record AEs as reported by subject or observed by Investigator
- Review any concomitant therapy
- Schedule study visits for subjects

#### 9.6.5 Treatment (Visit 4)

Occurs at least 48 hours, up to 144 hours, after previous visit.

#### **Predose Assessments:**

- Perform and document physical examination and VS
- hCG [urine] for females of childbearing potential
- Perform and document clinical tumor measurement and tumor volume change from baseline criteria
- Perform and document visual oral examination and neck lymph node examination
- Administer oral anti-emetics (ondansetron or promethazine, the dose to be determined at the discretion of the PI) before the start of PRV111 treatment
- Photograph the tumor
- Draw blood for PK (-15 to 0 minutes predose)
  - Administer PE (refer to Pharmacy Manual for administration instructions) • document time of application
- Administer PRV111 patch(es) and document time of each application and removal
  - Document adherence of each patch

#### **Postdose Assessments:**

•

- Draw blood for PK 30±5 minutes, 60±5 minutes and 120±5 minutes
- VS shall be monitored at 30±5 minutes, 60±5 minutes and 120±5 minutes following application of the last patch applied.
- Collect all used patches (include the ones that detached prematurely), record the time of the detachment of each patch, store the patches in the plastic bags supplied by the Sponsor (refer to Laboratory Manual for instructions).
- Record AEs as reported by subject or observed by Investigator
- Review any concomitant therapy
- Schedule study visits

#### 9.6.6 Post-Treatment/Pre-Op Visit (Visit 5)

- Occurs a minimum of 72 hours after the last visit and prior to surgery. Perform and document physical examination and VS
- Perform and document visual oral examination and neck lymph node examination
- •
- Perform and document clinical tumor measurement and Tumor volume CFB criteria
- ECG
- Collect clinical labs: blood draw for CBC, chemistry panel (creatinine, BUN, LFT, electrolytes [potassium, magnesium, calcium, and sodium], and perform urinalysis
- Photograph the tumor
- Record AEs as reported by subject or observed by Investigator
- Review any concomitant therapy

#### 9.6.7 Surgery Day (Visit 6)

- Tumor resection as per the standard of care
- Post-Surgery, collect clinical labs. Draw blood for CBC, chemistry panel (creatinine, BUN, LFT, electrolytes [potassium, magnesium, calcium, and sodium], and perform urinalysis. Post-surgical labs may be used, if deemed appropriate by the Principal Investigator

#### 9.6.8 Post-Treatment Follow-Up (Visits 7, 8, & 9)

All subjects will be followed for up to 6 months post-surgery at 3 visits: 1, 3, and 6 months postsurgery for loco-regional response and safety. Follow-up visits may coincide with standard of care follow-up visits, if deemed appropriate by the Principal Investigator.

- Perform and record results of physical examination and VS
- Perform visual oral examination and neck lymph node examination to assess for signs of loco-regional recurrence
- Review any concomitant therapy

#### 10 STATISTICAL METHODS AND PLANNED ANALYSES

#### **10.1** General Considerations

Clinical response to treatment will be evaluated according to Table 4.

#### **10.2** Sample Size Determination

Safety outcomes resulting in DLT will be used during the conduct of this study to select doses being tested according to pre-defined thresholds of toxicity.

- Local and systemic safety and tolerability will be summarized using descriptive statistics.
- The number of subjects with DLTs will be capped to be fewer than 2 subjects with DLTs out of 5 new subjects enrolled.
- The treatment regimen will be deemed tolerable if fewer than a third of the subjects exposed to it present DLTs.
- Efficacy based on Tumor volume CFB criteria will be summarized, and the null hypothesis that the probability of response is at most 30%, where a response is the occurrence of CR or PR will be tested using a one-sided test exact binomial test at level 0.018.
- •
- Variables measuring technical success (including residual cisplatin level in the patch) will be summarized using descriptive statistics.

At the end of Stage 2, the following is a statistical analysis of the sample size as it pertains to efficacy:

### Power and Sample Size

Based on Simon's 2-stage procedure, the null hypothesis that the true response rate is 0.30 will be tested against a 1-sided alternative. In the first stage, 5 evaluable subjects will be accrued. If there are 2 or fewer responses in these 5 subjects, the dose will be escalated. Otherwise, the dose will remain the same or de-escalated based on safety data. Additional subjects will be accrued for a total of 11 evaluable subjects at the final dose. The null hypothesis will be rejected if 7 or more responses are observed at the final dose. This design yields a type I error rate of 0.018 and power of 96.44% when the true response rate is 0.85.

Null response rate: P 0	Alt. response rate: P 1	Alpha one-tailed	Power	nl	rl	N	R
0.30	0.85	0.018	96.44%	5	2	11	6

N is the total number of evaluable subjects at the final dose

 $n_1$  is the number of evaluable subjects accrued during Stage 1

 $r_1$ , if  $r_1$  or fewer responses are observed during stage 1, escalate the dose if safety requirements are met

**R**, if R or fewer responses are observed by the end of Stage 2 in N subjects, then an effective dose is not found

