#### **Stopping Rules at Stage 2b:**

If 3 subjects with DLTs, no additional subjects will be dosed.

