#### 10.3 Note: If the dose is not increased after Stage 1, the test will be performed using all evaluable subjects from Stage 1 and 2. If the dose is adjusted after Stage 1, the test will be performed using all evaluable subjects from Stage 2.Pharmacokinetics

#### **10.4 Study Populations**

#### 10.4.1 Safety Population

All subjects who have at least 1 PRV111 patch applied will be included in the Safety Population.

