3.1.2 Primary Efficacy Analysis

[figure not shown]
[figure not shown]
[figure not shown]
The primary efficacy variable is response according to the Tumor Volume criteria per agreement from the FDA. (Section 7.3.1), where a response is CR, SR or PR (ORR; Objective Response Rate) and a non-response is SD or PD (See Efficacy Criteria table). The primary analysis is the analysis using the Efficacy Population and tumor volume change from baseline (CFB). Include 95% CI for CFB tumor size. The study will be deemed a success if at least 7 of the up to 11 evaluable subjects achieve a minimum of a PR.

[figure not shown]
Change of tumor volume will be summarized for each visit, however the final efficacy determination will be based on CFB from V1 to V5.

[figure not shown]
A frequency distribution of efficacy based on overall response rate (ORR) at each visit will be provided evaluable population. A one-sided test of response (CR, PR, SR) rate less than 30% will be calculated at each visit.

Photographs from V1 vs V5 will be presented

[figure not shown]

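### The stated type I error of 0.018 and power of 96.44% leave out the escalation path, and 7 of 11 responses (p = 0.0216) fails a plain exact binomial test at 0.018

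*Protocol*

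**What the plan says.** Protocol 10.2 (Power and Sample Size), repeated in the synopsis, bases the efficacy test on Simon's two-stage procedure with a null rate of 0.30, n1 = 5, r1 = 2, N = 11 and R = 6, and states: "This design yields a type I error rate of 0.018 and power of 96.44% when the true response rate is 0.85".

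- **Stage 1 boundary.** "If there are 2 or fewer responses in these 5 subjects, the dose will be escalated", subject to the safety requirements. If 3 or more respond and DLTs allow, the dose stays the same and 6 more evaluable subjects are added.
- **Final rule.** "The null hypothesis will be rejected if 7 or more responses are observed at the final dose". SAP 3.1.2 agrees: "The study will be deemed a success if at least 7 of the up to 11 evaluable subjects achieve a minimum of a PR".
- **Named test.** Protocol 10.2 also says the null hypothesis "will be tested using a one-sided test exact binomial test at level 0.018". SAP 5.1 repeats this, and SAP 5.2.1 sets every hypothesis test at 0.018.
- **Who is tested.** The note printed with the Protocol 10.3 heading (also in the synopsis and SAP 5.1) says "If the dose is not increased after Stage 1, the test will be performed using all evaluable subjects from Stage 1 and 2", then "If the dose is adjusted after Stage 1, the test will be performed using all evaluable subjects from Stage 2".
- **SAP power sentence.** The SAP 5.1 text attaches 96.44% to a true rate of 0.65. The table beneath it, and the Protocol, have 0.85.

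**The concern.** In a Simon design, r1 is a futility boundary: at or below it the trial ends and the null hypothesis is not rejected. Here the same boundary opens a second opportunity to reject, in a fresh cohort. Error and power figures that count that outcome as a failure do not describe this plan. Under the null it is also the likelier outcome of Stage 1.

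The number 0.018 does two jobs as well. In the design table it is the attained error of the two-stage rule. In the list of analyses it reads as the level of an exact binomial test. With N = 11 the two readings part company at exactly 7 responses.

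The primary objective is to determine a safe and efficacious dose. At stake are the false-positive risk of that claim, the verdict when 7 of 11 respond, and the set of subjects analysed after a de-escalation.

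**Working it through.** **Inputs** (Protocol 10.2; SAP 5.1): p0 = 0.30, p1 = 0.85, n1 = 5, r1 = 2, N = 11, reject at 7 or more. X1 is the number of responses in the 5 Stage 1 subjects and X2 the number in the next 6.

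**1. Reproduce the stated figures.** With X1 ≤ 2 counted as the end of the trial without rejection, P(reject) = Σ over x = 3, 4, 5 of P(X1 = x) × P(X2 ≥ 7 − x).

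- p = 0.30: 0.1323 × 0.0705 + 0.0284 × 0.2557 + 0.0024 × 0.5798 = 0.0093 + 0.0072 + 0.0014 = **0.0180**
- p = 0.85: 0.1382 × 0.9527 + 0.3915 × 0.9941 + 0.4437 × 0.9996 = 0.1316 + 0.3892 + 0.4435 = **0.9644**
- p = 0.65: **0.607**, which is the power at the rate named in the SAP 5.1 text

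Both stated figures match. The single-stage rule of 7 of 11 gives 0.0216 and 0.9841 instead, so the published values are those of the design that stops for futility.

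**2. Add the escalation path (no DLTs).** P(X1 ≤ 2) = 0.8369 at 0.30 and 0.0266 at 0.85. For 11 new subjects, P(X ≥ 7) = 0.0216 at 0.30 and 0.9841 at 0.85.

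- 30% at both doses: 0.0180 + 0.8369 × 0.0216 = 0.0180 + 0.0181 = **0.0361**. Half of the error comes from the escalation path.
- Stage 1 dose at 20%, escalated dose at 30%: 0.0016 + 0.9421 × 0.0216 = 0.0220
- Stage 1 dose at 10%, escalated dose at 30%: 0.00002 + 0.9914 × 0.0216 = 0.0215 (0.02145 before rounding)
- 85% at both doses: 0.9644 + 0.0266 × 0.9841 = 0.9906

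**3. The rule against the named test.** Plain exact binomial at 0.30: 7 of 11 gives p = 0.0216 and fails 0.018; 8 of 11 gives p = 0.0043 and passes. The joint chance of exactly 7 of 11, where the two rules disagree, is:

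| True rates | Same-dose path | Changed-dose path |
|---|---|---|
| 85% at both | 0.043 | 0.0266 × 0.0536 = 0.0014 |
| 65% at both | 0.195 | 0.2352 × 0.2428 = 0.057 |
| 30%, then 85% | – | 0.8369 × 0.0536 = 0.045 |

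Overall error (30% at both doses, no DLTs) according to which rule governs:

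- 7 of 11 on both paths: 0.0361
- 8 of 11 after a dose change only: 0.0180 + 0.8369 × 0.0043 = 0.0216
- 8 of 11 on both paths (plain binomial at 0.018): 0.0041 + 0.8369 × 0.0043 = 0.0077. Same-dose power at 0.85 then falls from 96.4% to 92.1%.

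**4. De-escalation and DLTs.** A de-escalated dose is both adjusted and not increased, so the two sentences of the note give it different analysis sets. The documents state no DLT rate, so the rates below are assumed. The error was computed by exact recursion over the Stage 1, 2a and 2b DLT rules in Protocol 6.1, including "If 3 subjects with DLTs, no additional subjects will be dosed".

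Assumptions: 30% response at every dose; one DLT rate at all doses, independent of response; all 5 Stage 1 subjects dosed and evaluable; 5 then 6 subjects per dose; 2 or more DLTs in Stage 2a treated as 2; the 3-DLT stop counts Stage 2b only; responses before a stop are counted; Stage 1 pooled with 6 later subjects if Stage 2a DLTs return the trial to the original dose.

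| Subjects tested after de-escalation | DLT 0% | 5% | 10% | 20% | 30% |
|---|---|---|---|---|---|
| Stage 2 only | 0.036 | 0.035 | 0.033 | 0.025 | 0.016 |
| Stage 1 pooled, 11 in total | 0.036 | 0.035 | 0.034 | 0.027 | 0.019 |
| Stage 1 pooled with 11 from Stage 2, cut-off still 7 | 0.036 | 0.038 | 0.043 | 0.050 | 0.048 |

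**The case against.** **The error is meant per dose.** The null hypothesis is tested at the final dose, and only one dose is ever tested. With 30% at both doses, each dose is falsely declared with probability 0.018 (0.0180 and 0.0181), and the error for the escalated dose cannot exceed 0.0216, an excess of at most 0.0036. This is fair, and 0.036 should be described as the chance of a false claim at either dose. But the Protocol credits 0.018 to the design without limiting it to a branch, the changed-dose test itself exceeds it, and the objective is to find a dose.

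**The numeric rule is explicit.** Seven or more, R = 6 and the SAP success criterion all agree, and 0.018 is most naturally the attained level of that rule under Simon's procedure. On the same-dose path this is a good answer, but no passage says that the exact binomial test is the two-stage calculation. On the changed-dose path there is no interim stop within the tested cohort, so the answer is not available.

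**The pooled readings are strained.** Protocol 10.2 counts responses at the final dose, and Stage 1 subjects were not treated at a de-escalated dose. That favours testing Stage 2 only. Pooling is nevertheless what the first sentence of the note literally requires. The DLT figures also depend on undocumented choices: at a 20% DLT rate, testing 11 new subjects after a return to the original dose moves 0.0248 to 0.0267. They should be read as a range.

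**The power figure is conservative.** This is correct: with 85% at both doses and no DLTs, success at either dose has probability 99.1%.

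**Conclusion.** The concern holds. The 0.018 and 96.44% are correct for the same-dose branch and for nothing else in the plan. With 30% response at both doses and negligible DLTs, the escalation path is taken 84% of the time and the overall error is 0.036. It is about 0.022 if the Stage 1 dose is at 10–20% and the escalated dose at 30%. With DLTs, the overall error runs from 0.016 to 0.050 over assumed rates of 5–30% and the three readings of the analysis set, so 0.036 is not a ceiling under every reading and 0.018 is not always exceeded.

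Three defects do not depend on the DLT rate:

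- The changed-dose test has size 0.0216 against a stated level of 0.018, so 7 of 11 yields opposite verdicts there. It does so on the same-dose path too unless the test is defined as the two-stage calculation.
- The analysis set after a de-escalation is contradictory.
- The 0.65 in the SAP 5.1 text is wrong for the power beside it.

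These affect the primary test and should be settled before the data are analysed.

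**What to change.** 1. Label 0.018 and 96.44% as same-dose-branch figures. Beside them give the 0.0216 size of the changed-dose test, the overall error of 0.036 (30% at both doses, no DLTs) with a DLT range and its assumptions, and the chance of success at either dose of about 99% (85% at both, negligible DLTs).
2. State one decision rule per path, identically worded, in the Protocol synopsis and 10.2 and in SAP 3.1.2, 5.1 and 5.2.1. Same dose: reject at 7 of 11, with 0.018 defined by the two-stage calculation. Changed dose: either keep 7 of 11 and state its level as 0.0216, or require 8 of 11 (p = 0.0043; overall error 0.0216 with no DLTs).
3. Reconcile the two sentences of the note, wherever they appear, on who is tested after a de-escalation, and give the number of subjects and the response cut-off for that test.
4. Correct 0.65 to 0.85 in the SAP 5.1 text.
5. In the same pass, reconcile SAP 2.2, which still has 16 evaluable subjects at the final dose and, in its de-escalation rules, 6 evaluable subjects in Stage 1, with N = 11 and n1 = 5.

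The cost is wording, with no extra subjects and a less favourable reported error. If 8 of 11 is chosen after a dose change, the chance of correctly declaring an escalated dose at true rates of 30% then 85% falls from 0.8369 × 0.9841 = 82% to 0.8369 × 0.9306 = 78%.

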#### 10.3 Note: If the dose is not increased after Stage 1, the test will be performed using all evaluable subjects from Stage 1 and 2. If the dose is adjusted after Stage 1, the test will be performed using all evaluable subjects from Stage 2.Pharmacokinetics

#### **10.4 Study Populations**

#### 10.4.1 Safety Population

All subjects who have at least 1 PRV111 patch applied will be included in the Safety Population.

#### 10.4.2 Evaluable Population

All subjects who have met the inclusion and exclusion criteria, and have completed at least 75% of the total dose required for that stage will be included in the Evaluable Population. This population will be used for the efficacy analysis.

#### **10.5** Statistical Analyses

#### 10.5.2 Subject Accountability, Demographics, and Baseline Characteristics

Subject completion status, dose modification, and study terminations will be summarized for each of the study stages and for the study overall. Subjects with major protocol violations will be listed. Demographics will be summarized along with baseline characteristics such as medical history, and baseline physical examination, weight, VS, ECOG PS, and concomitant therapy.

#### 10.5.3 Primary Endpoints

The primary endpoints for the study involve determination of a safe and efficacious dose of PRV111 (Cisplatin Transmucosal System) (cisplatin drug-loaded patch + PE) under the conditions of the trial.

Therefore, the primary endpoint is based on the incidence of DLTs and tumor volume CFB.

#### 10.5.4 Secondary Endpoints

Based on secondary objectives, the secondary endpoints are:

- Evaluate tumor response
  - 0
  - 0
- Assess short and long-term safety of the treatment
  - Loco-regional control: subjects will be followed-up for disease recurrence and safety following surgery
  - Incidence of recurrence at 6 months
- Total platinum assessment in blood, tumor and lymph nodes (if available)
- Technical success:
  - o Successful adhesion of the patch to the target lesion
  - Successful delivery (including release and permeation) of the drug to the target lesion, without getting to surrounding oral surfaces
  - Successful peel of the used patch after 10 minutes without damaging the target lesion underneath
  - Adhesion of the backing to the polymeric matrix embedded CLPs
  - Taste of the PE solution
  - Taste of the PRV111 patch
  - o Residual cisplatin level in the patch after the application period

#### 10.5.5 Efficacy Data

Efficacy outcomes include:

- Response to treatment evaluated by Tumor volume change from baseline (CFB)
- •
- Incidence of recurrence at 6 months

## 10.5.6 Safety Data

Safety observations and measurements including study drug exposure, AEs, laboratory data, physical examination findings, VS, weight, and concomitant therapy will be summarized and presented in tables and listings.

Laboratory parameters will be summarized using descriptive statistics and data listings. The incidence of clinically significant abnormalities will be summarized. Physical examinations, VS, and weight will be summarized by changes from baseline values using descriptive statistics.

AEs occurring after the start of treatment are TEAEs. The severity of the TEAEs will be graded according to the CTCAE criteria, version 4.03. The severity of oral mucositis will be graded according to the WHO grade (Section 8.2).

The number and percentages of subjects experiencing TEAEs will be tabulated by system organ class and preferred term. Assessments of TEAEs will include characterization of the type, incidence, severity, seriousness, and relationship to treatment. Summary subject listings will be provided for subjects with dose modification, SAEs, TEAEs resulting in study discontinuation, and deaths. The rates of local tolerability and oral mucositis will be reported.

